#### **6.6.4 *Re-hemorrhage/Re-treatment***

The difference in the rates of re-hemorrhage and re-treatment will be compared between randomization groups over the full duration of follow-up. Patients who withdraw consent or are lost-to-follow up will be censored at the time of study exit. Time to event will be computed as the date of the event (or the date of censoring) – randomization date. In cases where the patient has the event or is censored the day they are randomized, the time will be coded as 0.5 days. Re-hemorrhage or re-treatment may not occur because death from any cause precedes the event; thus, it is possible that censoring patients at all-cause mortality will lead to biased estimates when analyzing time to first event. Therefore, competing risks analysis using the methods of Fine and Gray (Fine & Gray 1999) will be used to estimate group differences for each endpoint.

#### **6.6.5 *Packing Density***

The mean packing density will be compared between groups using a T-test and summarized as the mean difference and corresponding 95% confidence interval. Missing packing density data will not be imputed and analyses will be based on all available data.

### **6.7 Analyses of Secondary Safety Endpoints**

All secondary safety endpoints will be analyzed using the safety population.

#### **6.7.1 *Adverse Events Reporting***

All adverse events, serious and non-serious, will be summarized in tabular form for reporting to the DSMB. Adverse events will be tabulated by seriousness, severity and relatedness to the investigational agent or the aneurysm.

#### **6.7.2 *Serious Adverse Events***

Serious adverse event rates will be calculated as the ratio of the total number of events over study follow-up days divided by total patient-time at risk for the specific event. Patient time at risk will be defined as the duration in which the patient is enrolled in the study since their date of randomization, inclusive of the day they were randomized [Time in study = (Study end date – Randomization date)+1]. Poisson models with robust variance estimation will be used to compare serious adverse events between randomization groups.

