#### 7.1.3 Reporting

All adverse events must be recorded on the Event eCRF with the following information:

1. Whether it was anticipated
2. Its relationship to the procedure, clinical course of the disease, device, or non-procedure
3. Outcome/Patient status
4. Treatment provided
5. Whether an action was taken and a description of said action

All serious adverse events must also be recorded on the Event eCRF with the following additional information:

6. Type of Serious Adverse Event
7. Whether it was reported within 72 hours of becoming aware of the event
8. Whether it happened during the procedure
9. Background Information
10. Whether it will be reported to the local IRB
11. Territory where initial procedure occurred

12. Whether it was serious (not life threatening), serious (life threatening) or lead to death

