## 2. STUDY OBJECTIVES

### 2.1 Primary Objective

The primary objective of this trial is to evaluate the effectiveness and safety of larger diameter (0.014-0.0155 inch) coils compared to smaller diameter (<0.014 inch) coils for the endovascular treatment of mid-size aneurysms.

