#### 3.1.2 Randomization and Masking

Patients will be randomly assigned in a 1:1 allocation to receive either larger or smaller coils. Patient randomization will be stratified by clinical site, aneurysm status (recently ruptured versus not), and dome to neck ratio (wide neck versus not). Randomization will be performed centrally through a web-based data collection system that automates the delivery of the randomization assignments.

Investigators will not be blinded to treatment assignment due to the nature of the treatment intervention. Investigators will, however, be blinded to all data from other clinical sites. Clinical outcome assessments will be completed by certified research staff that are not part of the treatment team. All angiograms will be analyzed by a blinded angiogram core laboratory personnel who will be blinded to clinical outcomes. Trial oversight will be provided by an independent Data and Safety Monitoring Board (DSMB).

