### 5.3.1 Serious Adverse Events

- Incidence of SAEs through end of study follow-up

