## 6. STATISTICAL METHODOLOGY

### 6.1 General Principles

Study day will be calculated from the reference start date and will be used to show the study days of assessments and events. Reference start date is defined as the date of randomization unless otherwise specified.

Continuous variables will be summarized using the following descriptive statistics: number of non-missing values, means, standard deviations, medians, interquartile range, maximum, and minimum. Categorical variables will be summarized using number of non-missing values, counts, and percentages.

Rates of events will be calculated as the ratio of the total number of events recorded divided by the total patient-time. Total patient-time will be calculated by summing the time (in study time units, e.g., days or months) that patients were at risk for a specific event from the reference time point until either study exit or the end of the time period of interest. Rates and their 95% confidence intervals will be reported. Time-to-event variables will be summarized using the Kaplan-Meier method or, in the presence of competing risk, by cumulative incidence curves accounting for competing events as appropriate.

In the situation where an event date is partial or missing, study day, and any corresponding durations are to appear partial or missing in listings. If a partial event date is recorded (i.e. the month and year are known but not the day) and is necessary to calculate patient-time at risk or patient-time to the event, the missing event day will be imputed to the 15th day of the known month and year.

For any variable measured at multiple points in time, change from baseline will be calculated as the difference between the value of the variable at a specific point in time (e.g. 1 year) minus the baseline value. Relative change from baseline will be calculated as the value of a parameter at a specific point in time minus the baseline value of the parameter divided by the baseline value of the parameter. Percent change will be calculated as the relative change multiplied by 100.

All hypothesis testing will be conducted at the 0.05 two-sided significance level unless otherwise specified. P-values will be rounded to three decimal places. P-values less than 0.001 will be reported as <0.001 in tables. P-values greater than 0.999 will be reported as >0.999.

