### 6.5.2 *Determination of Sample Size*

Sample size calculations were based on the primary endpoint under the following assumptions and operating characteristics: a) 73% angiographic occlusion at the 12-18 month visit in patients receiving smaller coils (control arm); b) a 9% absolute improvement (to 82%) in the incidence of angiographic occlusion in patients receiving larger coils; c) Approximately 80% power on a two-sided proportion test; and d) a significance level of 0.05. A sample size of 650 (325 in each arm) will allow us to detect the specified effect size with adequate power. Sample size was calculated using the `power.prop.test` function in R (R Core Team 2021).

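### SAP 6.7.2 compares SAEs between arms only as an all-cause rate over full follow-up; add a day-30 comparison of procedure- or device-related SAEs

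*Combined protocol and SAP*

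**What the plan says.** The SAP's primary objective is "to evaluate the effectiveness and safety of larger diameter" coils against smaller ones, so safety is part of it. The one secondary safety endpoint, in SAP 5.3.1, is "Incidence of SAEs through end of study follow-up". Protocol 7.2.2 has SAEs reported whatever their suspected cause, from consent to the final visit.

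SAP 6.7.2 analyses this endpoint as follows: "Serious adverse event rates will be calculated as the ratio of the total number of events over study follow-up days divided by total patient-time". Time at risk runs from randomization to study end, and the arms are compared with a Poisson model with robust variance. The section does not restrict by relatedness or set a peri-procedural window. It refers to time at risk for a specific event, but lists no specific events.

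SAP 6.7.1 tabulates events by relatedness to the agent or the aneurysm, for the DSMB. It specifies no between-arm estimate and does not name the procedure.

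The data for a narrower comparison are collected. Protocol 7.1.3 puts each event's relationship to procedure, disease course or device on the Event eCRF and, for SAEs, "Whether it happened during the procedure".

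**The concern.** The arms differ in which coils are placed during one procedure. Many of the risks listed in Protocol 7.1.2 arise in or soon after it: perforation, dissection or rupture, clot formation, distal emboli, device malfunction. The planned test adds these events to every other SAE over 12 to 18 months, in a population that includes ruptured aneurysms up to Hunt and Hess grade 3. Unrelated events add variance and pull the rate ratio towards 1.

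The risk is one of interpretation. A null all-SAE result could be read as reassurance about the larger coils when the test had little chance of showing a procedural difference.

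**Working it through.** **The plan's own figure.** SAP 6.5.2: "A sample size of 650 (325 in each arm) will allow us to detect the specified effect size with adequate power". The inputs are 73% versus 82%, and SAP 6.1 says "All hypothesis testing will be conducted at the 0.05 two-sided significance level unless otherwise specified". For two proportions, power = Φ{[d√n − 1.96√(2p̄(1−p̄))] / √(p₁(1−p₁)+p₂(1−p₂))}.

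- With n = 325, d = 0.09 and p̄ = 0.775: (1.6225 − 1.96 × 0.5906)/0.5871 = 0.792, so power is 78.6%.
- This agrees with the stated approximate 80% (exactly 80% needs 337 per arm). It is the only power figure in the documents; none is given for SAEs.

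**Assumed inputs (not in the documents).**
- p: procedural SAE risk in the smaller-coil arm, 3% to 10%, doubled in the larger-coil arm, one event per affected patient.
- b: unrelated SAEs per patient, 0.1 to 1.0, the same in both arms, negative binomial with dispersion 1 (variance b + b²).
- 325 per arm and equal follow-up.

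**Pooled all-SAE test.** Each arm has mean m = b + q and variance V = b + b² + q(1−q), with q = p or 2p. The rate ratio is (b+2p)/(b+p). SE² of its log is V₁/(325m₁²) + V₂/(325m₂²). Power = Φ(z−1.96) + Φ(−z−1.96), with z = log ratio/SE.

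Example, p = 5%, b = 0.3:
- means 0.35 and 0.40, ratio 1.143, log ratio 0.1335;
- V₁ = 0.4375, V₂ = 0.4800;
- SE² = 0.01099 + 0.00923 = 0.02022, SE = 0.142;
- z = 0.939, power 16%.

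**Procedure-related proportion, perfect labelling.** For 5% versus 10%: (0.9014 − 1.96 × 0.3725)/0.3708 = 0.462, power 68%.

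**With mislabelling.** Assume 80% of affected patients are labelled correctly and 3% of the others are labelled wrongly. Then 5% becomes 0.8 × 0.05 + 0.03 × 0.95 = 6.85%, 10% becomes 0.8 × 0.10 + 0.03 × 0.90 = 10.7%, and power is 41%.

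| Procedural risk | Pooled, b = 0.1 | b = 0.3 | b = 0.6 | b = 1.0 | Related only, perfect labels | Related only, mislabelled |
|---|---|---|---|---|---|---|
| 3% v 6% | 16% | 9% | 7% | 6% | 45% | 22% |
| 5% v 10% | 32% | 16% | 10% | 7% | 68% | 41% |
| 6% v 12% | 41% | 20% | 12% | 8% | 76% | 50% |
| 8% v 16% | 59% | 30% | 17% | 11% | 88% | 67% |
| 10% v 20% | 73% | 42% | 23% | 14% | 95% | 80% |

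Simulation with the robust rate-ratio test agrees to within about two points (for 5% v 10%, about 8% to 31% across b). Across b = 0.1 to 1.0, a doubling from 5% to 10% reaches the pooled test as a rate ratio of only 1.33 to 1.05.

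**What the other planned comparisons cover.**
- SAP 6.6.1 compares 24-hour neurologic morbidity (NIHSS worsening of at least 4 points, early deaths counted) by relative risk. It misses later events, and serious vessel, renal or device events without that change. In SAP 6.8 it is formally tested only if the primary hypothesis is rejected. Protocol 6.1 schedules NIHSS from discharge onward, with none at screening or at 24 hours.
- SAP 6.6.2 gives procedure-related death within 30 days by arm, with relative risk and confidence interval. It covers fatal events only.

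**The case against.** The strongest reply is that the plan does compare procedural harm. Neurologic morbidity at 24 hours is named among the most clinically important secondary endpoints, and 30-day procedure-related death already combines relatedness with a day-30 window. Perforation, emboli or thrombosis that causes a stroke or death would largely appear there. Survival, mRS and re-hemorrhage are also compared by arm. This stands: a reader might infer that procedural harm rests on the pooled SAE test alone, and the SAP does not support that.

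Second, any power figure depends on chosen rates. This also stands. A reader might settle on a single low figure such as 10% to 20%, but the documents contain no SAE rate, procedural rate or dispersion. With few unrelated SAEs, the pooled test reaches 73% at 10% versus 20%.

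Third, an all-cause rate avoids attribution by investigators who, under SAP 3.1.2, know the assignment. This stands in part. Mislabelling that is equal in both arms costs power, as the table shows. Mislabelling that differs by arm could create or hide a difference. That is a reason to keep the all-cause rate and add any-cause SAEs to day 30; it does not justify leaving the procedural comparison out.

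**Conclusion.** The point holds in a limited form. The only planned between-arm SAE comparison pools all causes over full follow-up. That leaves non-fatal procedure- or device-related SAEs without a 4-point NIHSS change at 24 hours with no between-arm estimate.

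The direction is firm: the procedure-related comparison had more power in every setting tabulated, including those with the assumed mislabelling. The size is conditional on the assumptions listed above and should be quoted only as a range.

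The documents do not support demoting the all-cause rate, since the narrower endpoint trades dilution for unblinded judgement. The change is a cheap improvement; the planned all-SAE analysis is not invalid.

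**What to change.** In SAP 6.7.2, keep the all-SAE rate and add, by arm in the safety population:

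- the proportion of patients with at least one procedure- or device-related SAE from procedure start to day 30, with risk difference and 95% CI adjusted for rupture stratum, using the existing eCRF fields;
- beside it, the proportion with any SAE to day 30, because relatedness is judged unblinded.

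Also state what the specific event in 6.7.2 means. SAP 6.6.2 already uses a 30-day procedure-related window for death, and the SAP allows revision before data lock.

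The cost is SAP wording and one table from data already collected. There are two downsides. It is one more secondary comparison without multiplicity correction (SAP 6.8 already leaves other secondary endpoints uncorrected), and its main component rests on unblinded attribution. The power of the any-cause day-30 comparison cannot be worked out here, because the documents say nothing about the timing of unrelated SAEs.

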### **6.6.1 *Neurologic Morbidity***

The number and percentage of patients who experience neurologic morbidity at 24-hours post-operation will be reported by randomization group. The proportion of patients with neurologic morbidity will be compared between groups using a log binomial model and differences between the groups will be summarized using relative risk and the corresponding 95% confidence interval.

Patients that die within 24-hours will be counted as having neurologic morbidity. Survivors missing the 24-hour NIHSS assessment will have their neurologic morbidity outcome imputed via multiple imputation assuming that the data are missing at random. The imputation model will be stratified by randomization assignment and include age, sex, randomization strata for wide neck status, randomization strata for aneurysm status, aneurysm size, and baseline NIHSS. Since this model includes a mixture of variables types (i.e. continuous and binary), a fully conditional specification method will be used (Berglund 2014). Thirty datasets will be imputed and Rubin's methods will be used to combine them and estimate treatment effect (Rubin 1986).

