### **6.6.2 *Survival***

Survival over the full duration of follow-up will be described using Kaplan-Meier curves and compared between the randomization groups using a log-rank test. The hazard ratio and corresponding 95% confidence interval for death in the larger coil group compared to the smaller coil group will be estimated using a Cox proportional hazards model. Patients who withdraw consent or are lost-to-follow up will be censored at the time of study exit. Time to event will be computed as the date of death (or the date of censoring) – randomization date. In cases where the patient dies or is censored the day they are randomized, the time will be coded as 0.5 days.

Causes of death and relatedness to the procedure will also be described by randomization group. The number and proportion of patients that have a procedure related mortality within 30 days post-procedure will be presented by group and group differences will be summarized as a relative risk with the corresponding 95% confidence interval.

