### **6.6.3 *Modified Rankin Scale***

The number and percentage of patients in each mRS score category will be reported at the 3 to 6 month and the 12 to 18 month visits by group. For each visit, a Cochran-Mantel-Haenszel “shift” analysis (also known as van Elteren's test, Savitz 2007) will be used to evaluate differences in the mRS distribution between groups. The distribution of mRS

scores is expected to differ by aneurysm status. Analyses will be repeated separately by randomization strata for aneurysm status (recently ruptured vs. not recently ruptured).

Patients with missing mRS data at the 3 to 6 and/or 12 to 18 month visit will have their data imputed via multiple imputation assuming that the data are missing at random. The imputation model will be stratified by randomization assignment and aneurysm status and include age, sex, randomization strata for wide neck status, aneurysm size, and baseline mRS. Since this model includes a mixture of variables types (i.e. continuous, binary and ordinal), a fully conditional specification method will be used (Berglund 2014). Thirty datasets will be imputed and Rubin's methods will be used to combine them and estimate treatment effect (Rubin 1986).

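### The SAE comparison in SAP 6.7.2 names no stratification covariates; run as a two-group model it would be conservative and would lose modest power to detect an excess of harm

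*Combined protocol and SAP*

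**What the plan says.** - **Randomization.** Protocol 5.5 stratifies by recent rupture (within 15 days), trial phase and neck. SAP 3.1.2 lists clinical site, rupture status and neck. Rupture and neck are on both lists; phase and site are each on one.
- **Primary model.** SAP 6.5.1 fits a log-binomial model with terms for treatment, recent rupture and wide neck. It gives stratified randomization as the reason for the last two and explains why center is left out.
- **SAEs.** SAP 6.7.2: "Poisson models with robust variance estimation will be used to compare serious adverse events between randomization groups". No covariate is named.
- **24-hour neurologic morbidity.** SAP 6.6.1: the proportion "will be compared between groups using a log binomial model". Rupture and neck are listed for the imputation model, but no terms are listed for the analysis model.
- **Survival.** SAP 6.6.2: curves are "compared between the randomization groups using a log-rank test", with a Cox hazard ratio. No strata are named.
- **Re-hemorrhage and re-treatment.** SAP 6.6.4 plans "competing risks analysis using the methods of Fine and Gray". No covariates are named.
- **Rupture as a prognostic factor.** SAP 6.6.3 says the distribution of mRS "scores is expected to differ by aneurysm status" and repeats the mRS analysis by rupture status. No such statement is made about SAEs.
- **General rules.** SAP 6.1 has no default on adjusting for stratification factors. SAP 6.5.5 allows extra covariates only for the primary endpoint, and only after imbalance at the 0.01 level.

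**The concern.** Stratified randomization makes the arms nearly equal in their share of ruptured aneurysms. Differences in SAE rate between ruptured and unruptured patients therefore add little to the variability of the treatment contrast. A Poisson model with treatment alone does not know this. Its robust variance uses the total spread of counts, including the spread between strata, and so overstates the uncertainty. Robust variance corrects for overdispersion; it does not correct for this.

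A conservative error protects an efficacy claim, but in a comparison of harm it works the wrong way. Safety is part of the primary objective (SAP 2.1), and SAE incidence is the only endpoint listed as a secondary safety endpoint (SAP 5.3). Protocol 7.2.2 collects every SAE whatever its suspected cause, so events due to the hemorrhage itself enter the count. That makes a rate difference by rupture status plausible.

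**Working it through.** **1. The plan's own figure.** The only power statement is for the primary endpoint (SAP 6.5.2): "Approximately 80% power on a two-sided proportion test", "a significance level of 0.05", 73% versus 82%, 325 per arm. With a pooled proportion of 0.775:

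Power = Φ[(0.09 − 1.96·√(2·0.775·0.225/325)) / √((0.73·0.27 + 0.82·0.18)/325)] = Φ(0.0258/0.0326) = Φ(0.79) = 78.6%.

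This agrees with the stated figure. No power or precision is stated for SAEs or for the other endpoints discussed here.

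**2. Inputs for SAEs.** From the documents: 325 per arm, 1:1 allocation, two-sided 0.05. Assumed, because the documents do not give them: share ruptured p = 30-50%; mean SAEs per patient m₁ (ruptured) and m₀ (unruptured); within-stratum variance m + k·m² with overdispersion k = 1; equal follow-up; balance within rupture stratum; rate ratio of interest 1.4 (ln 1.4 = 0.3365).

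**3. Formulas.**
- Overall mean m = (1−p)m₀ + p·m₁
- Within-stratum variance W = (1−p)(m₀ + k·m₀²) + p(m₁ + k·m₁²)
- Between-stratum variance B = p(1−p)(m₁ − m₀)²
- Unadjusted SE of the log rate ratio: SEᵤ = √[2(W+B)/(325·m²)]
- Adjusted SE, which is also the true SD under balance: SEₐ = √[2W/(325·m²)]
- Null rejection, unadjusted: 2Φ(−1.96·SEᵤ/SEₐ)
- Power, unadjusted: Φ[(0.3365 − 1.96·SEᵤ)/SEₐ]; adjusted: Φ(0.3365/SEₐ − 1.96)

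**4. One case in full.** p = 0.4, m₁ = 0.8, m₀ = 0.2:
- m = 0.44
- W = 0.6·0.24 + 0.4·1.44 = 0.720
- B = 0.24·0.36 = 0.0864
- SEᵤ = √(1.6128/62.92) = 0.160; SEₐ = √(1.44/62.92) = 0.151, so SEᵤ is 5.8% too large
- Null rejection 3.8%; power 56.0% unadjusted and 60.4% adjusted

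**5. The range.**

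| SAEs per patient, ruptured/unruptured | Share ruptured | W | B | SEᵤ/SEₐ | Null rejection, unadjusted | Power, unadjusted | Power, adjusted |
|---|---|---|---|---|---|---|---|
| 0.6/0.3 (2×) | 30% | 0.561 | 0.019 | 1.017 | 4.6% | 59.5% | 60.8% |
| 0.6/0.3 (2×) | 50% | 0.675 | 0.023 | 1.017 | 4.6% | 63.9% | 65.1% |
| 0.8/0.2 (4×) | 30% | 0.600 | 0.076 | 1.061 | 3.8% | 51.0% | 55.7% |
| 0.8/0.2 (4×) | 50% | 0.840 | 0.090 | 1.052 | 3.9% | 60.9% | 64.8% |
| 1.5/0.25 (6×) | 30% | 1.344 | 0.328 | 1.115 | 2.9% | 55.0% | 63.8% |
| 1.5/0.25 (6×) | 50% | 2.031 | 0.391 | 1.092 | 3.2% | 68.9% | 75.0% |

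**6. Simulation check.** Blocks of 4 within rupture-by-neck strata, 40% ruptured, robust Poisson with and without the two factors, 1,000 runs per setting. With k = 1, power for a rate ratio of 1.4 rose from 55.7% to 56.4% at 2× and from 62.1% to 67.3% at 4×. At 4× with no overdispersion and no treatment effect, the unadjusted SE averaged 0.127 against an actual SD of 0.112. Across the null settings, rejection was 2.8-5.0% unadjusted and 3.7-5.9% adjusted. With 1,000 runs, simulation error around 5% is 1.96·√(0.05·0.95/1000) = 1.4 points, so the adjusted figures are compatible with 5%.

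**7. Sensitivity to overdispersion.** At 1.25/0.25 (5×) with 40% ruptured, SEₐ/SEᵤ is 0.855 for k = 0, 0.919 for k = 1 and 0.944 for k = 2. The unadjusted SE is then 17%, 9% or 6% too large.

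**8. The other endpoints.**
- *24-hour morbidity.* SEₐ/SEᵤ = √[1 − B/(r(1−r))], where r is the overall risk. With 40% ruptured and risks of 20% and 5%: r = 0.11, B = 0.24·0.15² = 0.0054, r(1−r) = 0.0979, ratio 0.972. Over assumed overall risks of about 2-13% the SE falls by 0.1-3%.
- *Survival.* In simulated Cox models, adding rupture and neck left the SE unchanged (0.338 vs 0.338; 0.254 vs 0.254; 0.168 vs 0.169). Power for a hazard ratio of 1.75 rose from 36.7% to 37.8%, 56.3% to 59.4% and 89.1% to 91.4%, because the log hazard ratio moved slightly away from zero.
- *Fine-Gray.* Not simulated.

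**The case against.** The strongest reply is that the SAP is silent, not wrong. None of the four sections says its analysis is unadjusted. SAP 6.5.1 introduces its equation as the basic form of the log-binomial models, in the plural and with the rupture and neck terms, so the 24-hour morbidity model may already be covered. This stands for morbidity, where the text is ambiguous. It does not help the SAE model, which is Poisson and has no such form elsewhere in the SAP.

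A second reply is that the size is assumed. The documents give no SAE rates, rupture share or overdispersion, and the one statement about rupture and outcome concerns mRS. That also stands: at a two-fold difference the gain is about one power point, and gains near nine points need a six-fold difference. The direction does not depend on the assumed rates, provided the SAE rate differs by stratum.

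Third, SAEs lie outside the hierarchy in SAP 6.8, no power was planned for them, and the DSMB works from tabulations and interim mortality and complication data. This limits the consequence to the final SAE comparison.

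A reader might infer more: that the error bars are too wide for all four comparisons, or that the SAE result would be biased. Neither is supported. Adjustment did not narrow the Cox interval, Fine-Gray was not examined, and the morbidity effect is a few percent at most. With a log link and a constant rate ratio, adjusted and unadjusted Poisson models estimate the same quantity.

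**Conclusion.** The point holds for SAEs. As written, SAP 6.7.2 is most naturally run as a two-group comparison, which ignores the balance created by the trial's own stratification. With ruptured patients at 2 to 6 times the SAE rate, 30-50% ruptured and overdispersion 1, the SE is about 2-12% too large and power for a rate ratio of 1.4 is about 1 to 9 points lower. Less overdispersion makes the excess larger, more makes it smaller. The error is conservative: no bias in the rate ratio and no type I inflation.

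For 24-hour morbidity the effect is small. The model still deserves a clear statement because it tests H2, which must be passed before any mRS hypothesis is tested (SAP 6.8). For survival and re-hemorrhage/re-treatment the issue is one of definition: a stratified or adjusted hazard ratio is a different estimand from the unadjusted one, and the SAP does not say which is meant. The Cox power gain is only 1-3 points.

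This is an improvement that should be made before lock. It does not threaten the validity of the trial.

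**What to change.** 1. **SAP 6.7.2.** Add recent rupture and wide neck as covariates in the robust Poisson model. Keep the unadjusted rates by arm as descriptive.
2. **SAP 6.6.1.** State that the morbidity model uses the same two terms as the form in SAP 6.5.1. Name a fallback, such as Poisson regression with robust variance, if the log-binomial model does not converge.
3. **SAP 6.6.2 and 6.6.4.** State whether the log-rank, Cox and Fine-Gray analyses are stratified by rupture, and so which hazard ratio is the target.
4. **Protocol 5.5 and SAP 3.1.2.** Reconcile the two lists of stratification factors (trial phase on one, site on the other), so that the covariates follow the randomization actually used.

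The cost is a few sentences in the SAP, which allows revision before data lock, and two model terms. Rupture status and neck category are already recorded for randomization, so no new data are needed.
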